11.0 Potential Benefits to Subjects and Others

11.1 Potential Benefits to Subjects

Describe the potential benefits that individual subjects may experience from taking part in the research. If there is no direct benefit to subjects, indicate as such. Compensation is not considered a benefit. Compensation should be addressed in section 13.0.

Participants in the active stimulation arm may see less atrophy of calf muscles, better biomechanical properties of the healing tendon, and better function of the lower leg

11.2 Potential Benefits to Others

Include benefits to society or others.

The results of this research may benefit future patients undergoing tendon repair

12.0 Sharing Results with Subjects

Describe whether results (study results or individual subject results, such as results of investigational diagnostic tests, genetic tests, or incidental findings) will be shared with subjects or others (e.g., the subject's primary care physicians) and if so, describe how information will be shared.

Incidental findings from ultrasound imaging or research team evaluations will be communicated to the participant and to the treating physician (surgeon).

13.0 Subject Payment and/or Travel Reimbursements

Describe the amount, type (cash, check, gift card, other) and timing of any subject payment or travel reimbursement. If there is **no** subject payment or travel reimbursement, indicate as not applicable.

Extra or Course Credit: Describe the amount of credit **and** the available alternatives. Alternatives should be equal in time and effort to the amount of course or extra credit offered. It is not acceptable to indicate that the amount of credit is to be determined or at the discretion of the instructor of the course.

Approved Subject Pool: Indicate which approved subject pool will be used; include in response below that course credit will be given and alternatives will be offered as per the approved subject pool procedures.

Subjects will be compensated \$100/visit for the visits in weeks 2, 4, 6 and 12. A total compensation of up to \$400 for their time and effort in participating in the study.

Participants will be compensated using the Greenphire Clincard.

14.0 Economic Burden to Subjects

14.1 Costs

Describe any costs that subjects may be responsible for because of participation in the research.

No additional costs to the participant are expected.

14.2 Compensation for research-related injury

If the research involves more than Minimal Risk to subjects, describe the available compensation in the event of research related injury.

If there is no sponsor agreement that addresses compensation for medical care for research subjects with a research-related injury, include the following text as written - DO NOT ALTER OR DELETE:
It is the policy of the institution to provide neither financial compensation nor free medical treatment for research-related injury. In the event of injury resulting from this research, medical treatment is

available but will be provided at the usual charge. Costs for the treatment of research-related injuries will be charged to subjects or their insurance carriers.

For sponsored research studies with a research agreement with the sponsor that addresses compensation for medical care for research-related injuries, include the following text as written - DO NOT ALTER OR DELETE:

It is the policy of the institution to provide neither financial compensation nor free medical treatment for research-related injury. In the event of injury resulting from this research, medical treatment is available but will be provided at the usual charge. Such charges may be paid by the study sponsor as outlined in the research agreement and explained in the consent form.

It is the policy of the institution to provide neither financial compensation nor free medical treatment for research-related injury. In the event of injury resulting from this research, medical treatment is available but will be provided at the usual charge. Costs for the treatment of research-related injuries will be charged to subjects or their insurance carriers.

15.0 Resources Available

15.1 Facilities and locations

Identify and describe the facilities, sites and locations where recruitment and study procedures will be performed.

If research will be conducted outside the United States, describe site-specific regulations or customs affecting the research, and describe the process for obtaining local ethical review. Also, describe the principal investigator's experience conducting research at these locations and familiarity with local culture.

Recruitment will happen at the bone and joint clinic (Hershey and State College). Ultrasound imaging will occur at [name], Hershey or the Biomechanics and Imaging Lab at [name], State College.

15.2 Feasibility of recruiting the required number of subjects

Indicate the number of potential subjects to which the study team has access. Indicate the percentage of those potential subjects needed for recruitment.

An i2b2 cohort assessment was conducted utilizing data within the Hershey Medical Center system. 45 unique individuals who meet the inclusion criteria above, from 01/01/2018 to 01/01/2019, were identified. It is expected that similar number will be available during the duration of the study.

15.3 PI Time devoted to conducting the research

Describe how the PI will ensure that a sufficient amount of time will be devoted to conducting and completing the research. Please consider outside responsibilities as well as other on-going research for which the PI is responsible.

The PI ([name]) will devote 25% of his time to this study.

15.4 Availability of medical or psychological resources

Describe the availability of medical or psychological resources that subjects might need as a result of their participation in the study, if applicable.

Resources of Penn State Hershey Medical Center are available

15.5 Process for informing Study Team

Describe the training plans to ensure members of the research team are informed about the protocol and their duties, if applicable.

Training of therapists and participants on applying the NMES protocol

NMES applied at home by the participants themselves are common clinical practice. Research team are trained to provide and monitor such interventions. Typically, research teams demonstrate the procedure to the participants, participants will perform the procedure by themselves, and the research team verifies that the procedure is applied properly and corrects any problems with the protocol. The research team will verify and adjust the protocol during subsequent visits scheduled as part of regular physical therapy visit.

Ultrasound Imaging.

[name] and [name] will agree on the protocols for ultrasound data collection according to the established protocols that have been used in previous studies [65]–[70].

Other data collection instruments

Members of the team will be trained on using REDCap which will be used to record other data collection instruments such as questionnaires and to store data from imaging session and functional tests.

16.0 Other Approvals

16.1 Other Approvals from External Entities

Describe any approvals that will be obtained prior to commencing the research (e.g., from engaged cooperating institutions IRBs who are also reviewing the research and other required review committees, community leaders, schools, research locations where research is to be conducted by the Penn State investigator, funding agencies, etc.).

[Type protocol text here or indicate as not applicable]

16.2 Internal PSU Committee Approvals

Check all that apply:

- Anatomic Pathology – Penn State Health only** – Research involves the collection of tissues or use of pathologic specimens. Upload a copy of “HRP-902 - Human Tissue For Research Form” in CATS IRB.
- Animal Care and Use – All campuses** – Human research involves animals and humans or the use of human tissues in animals
- Biosafety – All campuses** – Research involves biohazardous materials (human biological specimens in a PSU research lab, biological toxins, carcinogens, infectious agents, recombinant viruses or DNA or gene therapy).

- Clinical Laboratories – **Penn State Health only** – Collection, processing and/or storage of extra tubes of body fluid specimens for research purposes by the Clinical Laboratories; and/or use of body fluids that had been collected for clinical purposes but are no longer needed for clinical use. Upload a copy of “HRP-901 - Human Body Fluids for Research Form” in CATS IRB.
- Clinical Research Center (CRC) Advisory Committee – **All campuses** – Research involves the use of CRC services in any way.
- Conflict of Interest Review – **All campuses** – Research has one or more of study team members indicated as having a financial interest.
- Radiation Safety – **Penn State Health only** – Research involves research-related radiation procedures. All research involving radiation procedures (standard of care and/or research-related) must upload a copy of “HRP-903 - Radiation Review Form” in CATS IRB.
- IND/IDE Audit – **All campuses** – Research in which the PSU researcher holds the IND or IDE or intends to hold the IND or IDE.
- Scientific Review – **Penn State Health only** – All investigator-written research studies requiring review by the convened IRB must provide documentation of scientific review with the IRB submission. The scientific review requirement may be fulfilled by one of the following: (1) external peer-review process; (2) department/institute scientific review committee; or (3) scientific review by the Clinical Research Center Advisory committee. NOTE: Review by the Penn State Health Cancer Institute (PSCI) Protocol Review Committee or the PSCI Disease Team is required if the study involves cancer prevention studies or cancer participants, records and/or tissues. For more information about this requirement see the IRB website.

17.0 Multi-Site Study

If this is a multi-site study (i.e., a study in which two or more institutions coordinate, with each institution completing all research activities outlined in a specific protocol) and the Penn State PI is the lead investigator, describe the processes to ensure communication among sites in the sections below.

[Do not type here]

17.1 Other sites

List the name and location of all other participating sites. Provide the name, qualifications and contact information for the principal investigator at each site and indicate which IRB will be reviewing the study at each site.

University of Delaware

17.2 Communication Plans

Describe the plan for regular communication between the overall study director and the other sites to ensure that all sites have the most current version of the protocol, consent document, etc. Describe the process to ensure all modifications have been communicated to sites. Describe the process to ensure that all required approvals have been obtained at each site (including approval by the site's IRB of record). Describe the process for communication of problems with the research, interim results and closure of the study.

[name] and [name] will have a monthly zoom meeting during the course of the study. Otherwise, issues requiring more immediate attention will be communicated through email or phone calls.

17.3 Data Submission and Security Plan

Describe the process and schedule for data submission and provide the data security plan for data collected from other sites. Describe the process to ensure all engaged participating sites will safeguard data as required by local information security policies.

The data collection and submission will be done through RedCap. The same protocol will be used for both locations for a seamless data flow between sites.

17.4 Subject Enrollment

Describe the procedures for coordination of subject enrollment and randomization for the overall project.

Clinicians collaborating in the study will identify patients at the moment of diagnosis with a complete Achilles rupture and undergoing an Achilles repair surgery at the sports medicine clinic. Clinicians will hand out the study flier and briefly mention to the patient that they may be eligible for a research study. The flier will include a QR code that will direct patients to a YouTube video where more information about the study is provided. If the participant is interested, the PI and/or a member of the team will provide an electronic copy of the informed consent for the patient to read. At the post-surgery appointment, a member of the team will discuss any details of study with the participant and will answer any questions they may have. Then the screening questions will be asked, and participants will sign the informed consent if eligible to participate.

Participants will be randomly assigned to a NMES treatment or control group in a 1:1 ratio. The Statistician will be responsible for generating a master list for each site with patient codes will be prepopulated with randomly assigned treatments (NMES vs control). As recruitment is performed, patients will be assigned a code with the corresponding intervention. The randomization will be performed at a 1:1 ratio between control and stimulation group.

Method:

1. The Statistician will generate one mutual master list (for State College and for the University of Delaware).
2. The master list will be shared with the team members in charge of recruitment through REDCap.
3. Once a subject is recruited (screened and consented), the next available code from the list will be assigned.
4. The patient will be then notified of the type of treatment they will get.

The master list will be stored and available in REDCap.

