4.2 Recruitment process

Describe how potential subjects first learn about this research opportunity or indicate as not applicable if subjects will not be prospectively recruited to participant in the research. Subject recruitment can involve various methods (e.g., approaching potential subjects in person, contacting potential subjects via email, letters, telephone, ResearchMatch, or advertising to a general public via flyers, websites, StudyFinder, newspaper, television, and radio etc.). **DO NOT** include the actual recruitment material or wording in this protocol.

[Do not type here]

4.2.1 How potential subjects will be recruited.

Clinicians who agree to collaborate in the study will hand a flyer to participants diagnosed a mid-portion Achilles tendon rupture and ask them if they want to be contacted to know more about the study. Those expressing interest will be contacted by a member of the research team.

4.2.2 Where potential subjects will be recruited.

4.2.3 Recruitment will occur in the Bone and Joint clinic in a private room within the clinic When potential subjects will be recruited.

Participants meeting eligibility requirements will be approached in the Bone and Joint Outpatient Clinic and presented with the study opportunity prior or shortly (within a week) to their planned surgery date.

4.2.4 Describe the eligibility screening process and indicate whether the screening process will occur before or after obtaining informed consent. Screening begins when the investigator obtains information about or from a prospective participant in order to determine their

eligibility. In some studies, these procedures may not take place unless HIPAA Authorization is obtained OR a waiver of HIPAA Authorization when applicable for the screening procedures is approved by the IRB. [For FDA regulated studies, consent for any screening activities would need to be obtained prior to screening unless specifically waived by the IRB.]

Eligibility and screening questions will be asked after obtaining verbal consent. Those questions have been included in the document "Eligibility and screening questions" submitted with application

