20.4 Access to data and/or specimens

Identify who will have access to the data and/or specimens.

IRB authorized team members will have access to RedCap and OneDrive.

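### The ordered list of treatments is shared with recruiting staff and nothing hides the unused rows, so the next arm can be known before screening and consent in an unblinded trial.

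*Combined protocol and SAP*

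**What the plan says.** Sections 7.2, 7.4.3 and 17.4 all describe a master list of patient codes already filled with NMES or control. Section 17.4 gives the sequence. The statistician generates the list. Step 2 then reads: "The master list will be shared with the team members in charge of recruitment through REDCap". Step 3 reads: "Once a subject is recruited (screened and consented), the next available code from the list will be assigned". The section closes with: "The master list will be stored and available in REDCap".

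On enrolment, section 4.2 says of patients who have received a flyer: "Those expressing interest will be contacted by a member of the research team". Section 17.4 then has a team member discuss the study at the post-surgery appointment, after which "Then the screening questions will be asked, and participants will sign the informed consent if eligible to participate". Section 5.2.1 allows the approach either before surgery or within a week after it.

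On access, section 20.4 says: "IRB authorized team members will have access to RedCap and OneDrive". On blinding, section 7.4.5 answers that it does not apply, and section 7.1 gives the control group no NMES.

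On the number of lists, section 17.4 says two things: "The Statistician will be responsible for generating a master list for each site" and, a few lines later, "The Statistician will generate one mutual master list (for State College and for the University of Delaware".

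**The concern.** Concealing upcoming assignments is what keeps the decision to enrol a patient independent of the arm that patient would get. A team member who knows that the next row is NMES, or control, can be more or less persistent with a given patient, frame the study differently, or read a borderline exclusion differently. No misconduct is needed for this to bias the comparison.

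The later safeguards are thin. There is no sham and no blinding, and randomization is unstratified. Section 8.3 states no covariate adjustment for the primary odds ratio. Its chi-square and Cochran-Mantel-Haenszel checks could reveal imbalance on gender, activity or age, but they would not correct selection on prognosis that is not measured. If enrolment has depended on the arm, the analysis cannot undo it.

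**Working it through.** **1. Can the next arm be read before enrolment?** Setting the provisions side by side:

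| Question | What the text gives | Where |
|---|---|---|
| Are the arms already on the list? | Yes, pre-filled | 7.2, 7.4.3, 17.4 |
| Is the list used in order? | Yes, next available code | 17.4, step 3 |
| Who receives it? | Staff in charge of recruitment | 17.4, step 2 |
| When is a code assigned? | After screening and consent | 17.4, step 3 |
| When is the patient told? | At the week-1 visit | 7.2.1 |
| Are unused rows hidden from staff? | Not stated anywhere | – |
| Sealed envelopes, central service or one-at-a-time release? | Not stated anywhere | – |

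The two timing rules govern when a code is attached to a patient and when the patient hears of it. Neither limits what a list holder can read earlier. Taken literally, the next arm is readable before screening and consent.

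**2. What could that do to the primary result?** The plan has no figure for this, so there is none to reproduce. The following is illustration only.

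Inputs from the plan: 50% heel-rise success (8.2); 25 per arm enrolled, or 22 completing (8.2, 8.3); NMES is declared better if the lower 95% limit of the odds ratio exceeds 1 (8.3). Assumptions: no true effect, a Wald interval, and a prognosis gap *d* between the arms caused by selection.

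With *a* successes of *n* on NMES and *c* of *n* on control:

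- ln OR = ln[a(n−c) / (c(n−a))]
- SE = √[1/a + 1/(n−a) + 1/c + 1/(n−c)], with 0.5 added to every cell if any is zero
- declare NMES better if ln OR − 1.96·SE > 0

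The binomial probabilities of all outcomes that meet the rule are summed, with p₁ = 0.5 + d/2 (NMES) and p₂ = 0.5 − d/2 (control):

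| Gap *d* | p₁ / p₂ | 25 per arm | 22 per arm |
|---|---|---|---|
| 0 | 0.500 / 0.500 | 2.2% | 2.4% |
| 5 points | 0.525 / 0.475 | 4.9% | about 5% |
| 10 points | 0.550 / 0.450 | 9.6% | 9.5% |

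**3. How much steering would produce such gaps?** Assume half of patients have a 65% chance of success and half 35%, and that staff can tell them apart. A share *f* of the unwanted class is passed over. The favoured class then makes up g = 0.5 / [0.5 + 0.5(1−f)] of those enrolled. On NMES, p₁ = 0.65g + 0.35(1−g). On control, p₂ = 0.5 if only NMES places are steered, or 0.35g + 0.65(1−g) if both are. For example, f = 0.5 gives g = 0.5/0.75 = 0.667 and p₁ = 0.433 + 0.117 = 0.55.

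The willing, eligible candidates needed for 50 places are 25/(1 − f/2) + 25 if one side is steered, and 50/(1 − f/2) if both are.

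| Steered | *f* | Gap (points) | Wrongly declared better, 25 per arm | Candidates needed |
|---|---|---|---|---|
| NMES places only | 0.2 | 1.7 | 3.0% | 53 |
| NMES places only | 0.5 | 5.0 | 5.0% | 58 |
| NMES places only | 1 | 15.0 | 18.4% | 75 |
| Both | 0.2 | 3.3 | 3.8% | 56 |
| Both | 0.5 | 10.0 | 9.6% | 67 |
| Both | 1 | 30.0 | 55.0% | 100 |

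Section 15.2 counts 45 eligible patients in one year in the Hershey system. The last rows are therefore costly to reach and serve only to show the far end of the model.

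**The case against.** The strongest reply is that the text states sharing, while sight of future arms is inferred. REDCap can be set up to hide unused rows, and section 22.0 sends the data plan to a separate form that is not available here and might set access roles. Section 20.4 is weak support, since it belongs to the section on data kept for future research.

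There are also real protections. The statistician generates the list. Codes are assigned after consent. The clinicians who hand out flyers are not described as list holders. Screening uses a fixed set of questions (4.2), and most eligibility criteria are factual. Finally, nothing in the documents shows that staff could predict week-12 heel-rise this early, and modest one-sided steering moves the error rate only from 2.2% to about 3%.

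Much of this stands as context, and the larger steering figures should carry no weight in the rating. It does not remove the problem. The plan's own words describe the list as shared with recruiters and available, which is more than silence. If the data plan form does restrict access, 17.4 should say so. Section 20.4 is only supporting, though section 20.1 does include the master list among the data that section covers. Fixed questions do not govern who is pursued or how the study is presented, and exclusion 6 in section 3.2, the catch-all for conditions that limit walking or jumping, leaves room for discretion.

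**Conclusion.** The concern holds. Followed as written, section 17.4 leaves allocation unconcealed from the people who contact, screen and consent patients, in a trial without blinding. This needs correcting because of the stated access rule. It does not depend on showing that anyone would look ahead, and the documents do not say that anyone would.

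The size of the bias cannot be derived from the documents. Under the assumptions above, a prognosis gap of 5 to 10 points would roughly double to quadruple the chance of a false claim for NMES (4.9/2.2 ≈ 2.2; 9.6/2.2 ≈ 4.4). These are neither bounds nor forecasts.

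The inconsistency over the number of lists is real but secondary, and does not bear on concealment. State College may be meant to stand for the whole Penn State site, since 17.3 speaks of two locations. Even so, sections 5.2.1 and 15.1 also have patients recruited at Hershey, and the text does not say which list covers them.

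**What to change.** In section 17.4, replace step 2 with wording such as:

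> The Statistician loads the list into REDCap. Staff who recruit, screen, consent or enrol cannot view unassigned treatments. Each assignment is released one at a time, only after eligibility and signed consent are recorded for that participant.

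Replace the closing sentence on storage with:

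> The master list is stored in REDCap; only the Statistician can view unassigned rows.

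Other concealment arrangements would also serve, provided the text says that enrolling staff cannot see unassigned arms. Separately, reduce the two descriptions of the list to one scheme and state which list covers patients recruited at Hershey.

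The cost is two text replacements, one wording repair and a small set-up in a system already in use. No patients or visits are added. The one drawback is that the arm is not known ahead of the visit, so a device must be at hand at the week-1 visit. Table 3 already places consent, randomization and the NMES demonstration there, and section 7.2.1 has the patient told the assignment at that visit.
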